- **Feasibility:** We will compare user compliance in using the device in the treatment vs. control. Compliance will be assessed using self-reports. Participants will bring home a device usage log, record time at which they put on and take off the device every day, and submit the log during the weekly evaluation. Study personnel will record which hand the participant is wearing the device (right vs left) at the beginning of the weekly evaluation session. During their final session, participants will complete a technology acceptance questionnaire to evaluate their experience using the device. Additionally, a pedometer function will be run in the watch to obtain a total number of steps for a week, which can provide a rough estimate of the wear time. Participants will also wear the device while completing a 10-meter walk test during their initial visit. Walking speed and the pedometer reading will be recorded when the test is complete.
- **Safety:** We will compare the rate of occurrence of adverse events in the treatment vs. control condition. The measures of adverse events will include worsening of hand sensation, hand strength, hand dexterity, upper limb pain level, spasticity, and wrist skin irritation. Specifically, hand sensation will be assessed using the Monofilament Test, the Two-Point Discrimination Test, and verbal report of any numbness and tingling. Hand sensation will be determined to have deteriorated if any of these hand sensation test results declines by a category (e.g. "normal" to "diminished light touch" for the Monofilament Test with a change more than two points; "no" to "yes" for numbness and tingling). Hand strength will be determined to have deteriorated if grip strength declines by more than 20% from the baseline (which is approximately 2 standard deviation of the population grip strength data) and more than minimal

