detectable change (MDC) (also known as the smallest real difference, Chen et al 2009). Hand dexterity will be determined to have deteriorated if the Nine Hole Peg or Box and Block Test score worsens by more than 20% (approximately 2 standard deviation of the population data) and MDC (Chen et al 2009). Hand strength and dexterity measurement will be performed three times during the baseline testing. Upper limb pain will be assessed using the visual analog pain rating scale (0 to 10). Upper limb pain will be determined to have increased if the pain level indicated on the visual analog pain rating scale increases by more than 2. Spasticity will be show assessed using the Modified Ashworth Scale (MAS). Spasticity will be determined to have worsened if MAS increases by more than 1 point (equivalent to the effect size of botulinum toxin A). Wrist skin irritation and increased swelling, if there is any, will be noted. Rigorous safety criteria will be used in which adverse events will be noted if any of the measures (hand sensation, strength, dexterity, pain, spasticity, skin irritation, swelling) worsens at any of the four evaluation times compared to the baseline. The co-investigator and study neurologist, [name], will meet with each participant in person or via teleconference to interview the participant regarding safety related to wearing the device.

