10.0 Data Management

- **Confidentiality protection:** The data from test results will be de-identified once it has been collected and before it is stored. This means individual results would not be able to be linked to the participant by others who review the results of this research. The linkage between participant codes and identities as well as all other identifiable

information including consent forms will be stored in a locked room and be accessible only to the study personnel.

- Statistical analysis: For Primary Aim of feasibility and safety, we will compare rates of compliance and device-related adverse events between the treatment and control conditions using the test of non-inferiority. For safety, we will analyze the data using the “intent to treat” paradigm. The meaningful difference in adverse events to detect between the treatment and control is 20% for the following reason. For a regulatory approval, a safety level similar to a comparable FDA-approved device is desired. One such device, with availability of safety data, is a Bioness electrical stimulator for foot drop: It has a 21% higher likelihood for adverse events compared to a standard ankle foot orthosis (Kluding et al. 2013). Based on power analysis below, we will be sufficiently powered to statistically discern different rates of adverse events if more than 3 out of 24 participants experience adverse events in the treatment vs. control condition. In other words, if 3 or less participants out of 24 experience adverse events in the treatment vs. control condition, we will deem TheraBracelet safe for the purpose of an FDA approval. We will verify that there is no order effect using exact binomial tests.
- For feasibility, compliance will be defined as participants’ use of the device for at least half the prescribed time. The reason is that 4 hours/day is still a substantial use of this assistive device in daily living, and will provide sufficiently useful information about feasibility of TheraBracelet. Similarly with the analysis for safety, if 3 or less participants out of 24 are incompliant in the treatment vs. control, we will conclude that TheraBracelet is as feasible as wearing a non-vibrating wristband. The cumulative hours of device usage will also be examined for both conditions to inform the general usage trend.

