- For the secondary outcome of durability of TheraBracelet’s instant effect, the hypothesis will be tested using repeated measures ANOVA for each hand function measure, with factors of vibration (on/off), condition (treatment/control), evaluation time (1-5), and their interactions. A significant main effect of vibration, with improved hand function with vibration on vs. off, with non-significant interactions of vibration×evaluation time and vibration×condition, would indicate durability over a month. In contrast, a lesser extent or abolishment of the instant effect toward the later evaluations or for the treatment condition, with significant interactions of vibration×evaluation time or vibration×condition, would indicate desensitization. In that case, the time point at which the instant effect wanes will be examined using Tukey type posthoc pairwise comparisons.
- A possibility exists that instant enhancement of hand function with TheraBracelet may trigger more use of the affected hand in daily living, which, when accumulated over time, might lead to improvement of the innate hand function (without vibration). This is analogous to cane users who may walk more with canes than without, and thus build greater lower limb abilities over time. Thus, change in the innate hand function will be examined. A significant effect of condition×evaluation time, with greater improvement of the innate hand function for the treatment vs. control, will suggest a therapeutic effect of TheraBracelet for secondary investigation.
- Impact of TheraBracelet on activities of daily living and quality of life will be assessed using repeated measures ANOVA for the SIS and SS-QoL, with the main effect of condition.

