- Power analysis: The sample size for the primary outcome of safety was determined for testing hypothesis of non-inferiority using a 2×2 crossover at 80% power and 5% significance level. A sample size of 24 (12 in each condition at randomization) provides sufficient power to conclude non-inferiority within a difference in adverse events of 20% between the discordant pairs (those who are safe with control but unsafe with treatment vs. those with the opposite), assuming a total of 10% discordance rate (proportion of participants with different responses for the two conditions) and a 90% safe rate for the control. That is, we will be powered to statistically conclude non-inferiority (hence safety) if 3 or less out of 24 participants have adverse events in treatment vs. control. For the Secondary Aim involving repeated measures ANOVA, with the effect size of $f=0.25$ for the Box and Block from our previous study, (Seo et al., 2014) a sample size of 19 is needed assuming a conservative correlation of 0.3 across evaluation times, for 80% power and 5% significance level. Thus, we will aim to obtain data from 24 participants. Considering that some may be found ineligible after enrollment, a total of 30 recruitment is proposed.
- Data sharing: Only de-identified coded data will be reported and/or shared with the public in publications, in ClinicalTrials.gov, or upon written request.

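### The safety conclusion counts only individual threshold events, so a small to moderate average loss in the vibration month can pass as safe although the paired data would show it

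*Combined protocol and SAP*

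**What the plan says.** **Event definition (Section 9.0, Safety).** For grip, "Hand strength will be determined to have deteriorated if grip strength declines by more than 20% from the baseline" and also by more than the MDC. For the Nine Hole Peg and Box and Block tests, an event requires that the score "worsens by more than 20% (approximately 2 standard deviation of the population data) and MDC". Pain, spasticity and sensation have their own individual cut-offs. A participant has an event in a month if any measure "worsens at any of the four evaluation times compared to the baseline".

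**Safety conclusion (Section 10.0, Statistical analysis).** The plan will "compare rates of compliance and device-related adverse events between the treatment and control conditions using the test of non-inferiority". The working rule is that "if 3 or less participants out of 24 experience adverse events in the treatment vs. control condition, we will deem TheraBracelet safe". The Power analysis paragraph repeats this count and bases N = 24 on a 20-point margin "at 80% power and 5% significance level".

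**Nearest group-level analysis (Section 10.0).** Change in hand function without vibration is to be examined. A significant condition×evaluation time effect, "with greater improvement of the innate hand function for the treatment vs. control, will suggest a therapeutic effect", as a secondary investigation. No reading is given for a decline. Pain is not mentioned. Grip is uncertain: the Secondary Aim in Section 1.0 lists it among the instant-effect measures, but the Durability paragraph of Section 9.0 does not.

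**The concern.** The primary question is whether a month of daily vibration worsens the hand. Section 12.0 says that nothing is known about side effects of such use, so a modest effect shared by most users cannot be ruled out in advance.

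The MDC says when one person's change exceeds measurement error. The 20% figure is justified by population spread. Both are tolerances for individuals, and neither shows that a smaller shift in the group average is harmless. The crossover gives each participant a treatment-minus-control change, from a baseline and four weekly visits in each month. That is the most sensitive information on harm the trial collects, and the safety conclusion does not use it. At stake is a safety statement, intended to support regulatory approval, made beside data that show a functional loss, with no agreed way of handling it.

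**Working it through.** **1. The plan's own figure.** Inputs from the Power analysis: N = 24, margin 0.20, discordance 10% (5% each way if there is no difference), 80% power, 5% level. The level's sidedness is not stated; one-sided is assumed. A paired score test with exact trinomial power gives 76.2% at N = 22, 83.2% at N = 23 and 82.4% at N = 24. The planned 24 is reproduced to within one participant. At N = 24 the test passes with at most 1 treatment-only event if there are no control-only events. The count rule, read as an excess of 3 or fewer, is looser, so both are shown below.

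**2. A hand check.** Assume a uniform 10% loss on one measure, a change-score SD of 5% and a 20% threshold. At one visit an event needs a further (20 − 10)/5 = 2 SD. Over four correlated visits (r = 0.5, from the shared baseline) the simulated event rate is 7.2% in the treatment month and about 0 in the control month.
- Test passes: 0.928^24 + 24 × 0.072 × 0.928^23 = 0.166 + 0.310 = 0.476 (simulated 0.477).
- Count rule passes: 0.476 + 276 × 0.072² × 0.928^22 + 2024 × 0.072³ × 0.928^21 = 0.476 + 0.276 + 0.157 = 0.91 (simulated 0.911).
- Paired mean: error variance 12.5 per reading, so SD of the difference = √[2 × (12.5 + 12.5/4)] = 5.59, standard error 5.59/√24 = 1.14, and t is about 10/1.14 = 8.8. Detection is practically certain.

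**3. A range of measurement error.** Simulation, 20,000 trials per cell, N = 24, one measure affected, treatment month only. Baseline is the mean of three readings, followed by four single weekly readings. Event threshold = max(20%, MDC), with MDC = 1.96 × √2 × SEM. This is 19.4% at SEM 7% and 27.7% at SEM 10%, so it raises the threshold only in the last column. For the paired interval, SD of the difference = √[25 + 2 × SEM² × (1/3 + 1/4)], where 25 allows for a 5-point spread between people. The 95% half-width is then 2.069 × 6.61/√24 = 2.8 points at SEM 4% and 2.069 × 11.90/√24 = 5.0 points at SEM 10%.

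| SEM, % of baseline (assumed) | 4 | 5 | 6 | 7 | 10 |
|---|---|---|---|---|---|
| 8% loss: test says safe | 93% | 51% | 16% | 5% | 22% |
| 8% loss: count rule says safe | 99.9% | 92% | 58% | 29% | 65% |
| 8% loss: paired CI shows worsening | 100% | 99.9% | 99.6% | 98.5% | 88% |
| 5% loss: test says safe | 99.8% | 93% | 65% | 36% | 53% |
| 5% loss: paired CI shows worsening | 94% | 89% | 81% | 73% | 50% |

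At a 15% loss the test says safe in under 1% of trials.

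**4. Several measures falling together.** With grip and both dexterity tests each losing 8% (independent errors), the test passes in 63/5/0.1/0/0.6% of trials over the same SEM values. At 10% it passes in 9% at SEM 4% and about 0% elsewhere. For a 5% loss on all three, under the error model of step 2 with change SD 5/7.5/10%, the test passes in 95/10/1.5% and the count rule in 100/45/19%.

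**5. A limit of step 3.** The 5-point spread was applied to the paired interval only. If individual losses vary that much, more people cross the threshold. At SEM 4% and a mean loss of 8%, the SD of one visit's change is 4 × √(4/3) = 4.62, and the crossing chance is P(Z > 12/4.62 = 2.60) = 0.5%. Adding the spread gives √(21.3 + 25) = 6.81 and P(Z > 1.76) = 3.9%. The pass rates above therefore describe a loss that is much the same in everyone.

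**The case against.** **The rule is a composite.** Any measure at any of four visits counts, so a general decline has many chances to register. This stands, and step 4 shows its force. A reader might infer that any systematic loss across all participants could be declared safe. The documents do not support that: the gap is confined to losses on one measure, losses of about 5% or less on several, or low measurement error.

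**A group-level analysis already exists.** The innate-function analysis would show a decline as readily as a gain, because the interaction test has no direction. Section 11.0 gives the unblinded DSMB aggregated safety data every three months, and Section 9.0 adds a neurologist interview. This stands in part. A reader might infer that the plan would hide a decline, or that it excludes reading one; the text supports neither. What is missing is narrower: a stated reading for a decline, a link to the safety conclusion, pain, and clear inclusion of grip. No group-mean criterion is given for the DSMB.

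**The largest figures rest on assumed SEMs of 4 to 5%, and the count-rule figures on one reading of an ambiguous sentence.** Correct. At SEM 6 to 10% the planned test passes an 8% single-measure loss in 5 to 22% of trials.

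**Event-type endpoints are legitimate in a small safety study.** Accepted; the event definitions need not change.

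**A veto whenever an interval excludes zero would be badly built.** Also accepted. It has no harm margin, would trigger in 22 to 57% of trials for a 3% loss on one measure, and favours imprecise data.

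**Conclusion.** The point holds within limits. The primary safety conclusion rests only on individual threshold events. A fairly uniform loss in the vibration month of about 5 to 8% of baseline on one measure, or about 5% or less on several, can be called safe although the paired crossover data would show it. Losses of about 15%, or of 8 to 10% on several measures together, are usually caught; the main exception is 8% on three measures at SEM 4%, where the test still passes in 63% of trials.

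The size depends on measurement error and MDC values that the documents do not give, on uniform losses, and on no background events from other measures. Pain was not simulated. If the MDC raised the effective threshold to 30% (assumed), the count rule would call a 10% single-measure loss safe in 92 to 100% of trials at change SDs of 5 to 10%.

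This is a gap in how existing data feed the conclusion. It is not evidence that the device is harmful, nor that the event definitions are wrong.

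**What to change.** 1. In Section 10.0, Statistical analysis, pre-specify as supporting safety evidence the treatment-minus-control difference in mean change from that month's baseline, over the four weekly visits and with vibration off, with a two-sided 95% confidence interval. Do this for grip strength, Box and Block, Nine Hole Peg and upper limb pain.
2. In the innate-function paragraph of Section 10.0, state that the condition×evaluation time result is read in both directions.
3. Require that any interval lying wholly on the worsening side be reported as a safety signal, with its estimated size, next to the safety conclusion. It should not overturn that conclusion automatically.

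The cost is SAP wording and four paired estimates from data already collected, with no new visits, measures or participants. The downside is false signals: each interval has a 2.5% chance of lying on the worsening side when there is no effect, so at most 4 × 2.5% = 10% overall. Because a signal is reported and not used as a veto, the power of the primary non-inferiority test is unchanged.

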- Secondary Aim: Determine the durability of TheraBracelet's instant effect over a month. TheraBracelet's instant effects will be quantified as an increase in the hand touch sensation score, dexterity score, and grip strength with vibration turned on vs. off (with 'on' and 'off' tested in a random order) in each weekly evaluation. Hypothesis: TheraBracelet's instant effects in improving hand function will persist across all weekly evaluations (i.e. desensitization to vibration will not occur during extended daily use over a one-month period). In addition, the broader impact of TheraBracelet will be assessed by comparing self-reported abilities for activities of daily living and quality of life between the treatment and control conditions.

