9.0 Study Design / Methods

- **Study design:** The study will use a 2×2 crossover design. Participants will be randomly assigned to either the treatment or control condition for the first month, followed by a 2-week washout period and then crossover to the other condition. For both conditions, participants will be instructed to wear TheraBracelet on the affected wrist every day for at least 8 hours/day during their daily activity over a month. The device will apply wrist vibration at 60% of the sensory threshold (imperceptible) for the treatment condition, and no vibration for the control condition. The control condition is needed to assess safety of TheraBracelet in comparison to that of simply wearing a wristband, thereby accounting for any worsening of symptoms that may occur as a natural course after stroke. Half the participants will start with the treatment and half with the control (balanced).
- **Schedule:** One person's participation will be 2.5 month long (= 1 month for one condition, 2 week washout period, 1 month for another condition). For each condition, participants will come to the laboratory once a week for evaluation for a total of 5 times: The 1st visit will entail the baseline evaluation followed by an introduction to using the device. Subsequent visits will be for evaluation after using the device each week. A follow-up assessment will be administered 4-16 weeks after the 10th session if any safety measure has worsened as defined as an adverse event by the 10th visit compared to the 1st visit. The follow-up assessment will evaluate only the measure that has worsened.
- Evaluation will include feasibility, safety, and durability, as detailed below.

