- **Durability:** The durability of TheraBracelet's instant effect will be examined by assessing TheraBracelet's instant effect in each weekly evaluation and comparing them across. The instant effect will be quantified as increase in the hand touch sensation (Monofilament Test) dexterity scores (Nine Hole Peg and Box and Block Tests) with vibration turned on compared to off, with the 'on' and 'off' tested in a random order, blinded, within a single evaluation session. If TheraBracelet's instant effect is seen for all evaluation times, it will support durability (i.e. desensitization to vibration does not occur). In addition, the impact of TheraBracelet on stroke survivors' self-reported abilities for activities of daily living and quality of life will be assessed. Specifically, the Stroke Impact Scale, SIS (sections of the hand, activities of daily living, and recovery), and Stroke Specific Quality of Life, SS-QoL (sections of the self-care and upper extremity function), will be obtained at weekly evaluations and compared between the two conditions. The Nine Hole Peg and Box and Block Tests will be videoed to ensure the exact start and stop time are recorded. This video will not include the participant's face in order to maintain confidentiality.
- **Protection against risk:** For fatigue, frequent sufficient breaks will be provided to participants. As for potential skin irritation due to wearing the wristband, the wristband tightness may be adjusted with a new wristband to maximize participant comfort. Participants will be notified if we learn anything that might make them change their mind about participating in the study. Potential risks of deterioration of hand sensation, strength, and dexterity, increased upper limb pain level and spasticity level, and/or wrist skin irritation will be monitored every week during the weekly evaluation when participants come to the laboratory. In fact, these events are the outcome measures of safety for the primary aim of the study. Participants will be informed that they can drop out of the study any time without penalty.

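### On/off test order is randomised but not stated to be balanced and is left out of the model, which costs power in the interaction tests on which durability rests

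*Combined protocol and SAP*

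**What the plan says.** The secondary aim (Section 1.0) measures the instant effect as on versus off, "with 'on' and 'off' tested in a random order) in each weekly evaluation". Section 9.0 (Durability) repeats that the two are "tested in a random order, blinded, within a single evaluation session". Neither place says that the order is balanced within a visit, a condition or a participant.

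Section 10.0 analyses each hand function measure by repeated measures ANOVA "with factors of vibration (on/off), condition (treatment/control), evaluation time (1-5), and their interactions". Test position (first or second in the session) is not among the factors. Durability is concluded from a significant vibration main effect together with non-significant vibration × evaluation time and vibration × condition interactions. A significant interaction is read as desensitisation and is followed by Tukey-type comparisons.

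Four other statements come close to the issue but do not settle it:

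- "Half the participants will start with the treatment and half with the control (balanced" (Section 9.0) concerns the treatment/control sequence.
- "We will verify that there is no order effect using exact binomial tests" (Section 10.0) belongs to the safety analysis, and a binomial test does not apply to continuous on/off scores.
- "For fatigue, frequent sufficient breaks will be provided to participants" (Section 9.0) addresses fatigue but not practice.
- "Hand strength and dexterity measurement will be performed three times during the baseline testing" (Section 9.0) appears under safety and applies to baseline only.

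**The concern.** The Nine Hole Peg and Box and Block tests depend on performance. The second attempt in a session may be better through practice or worse through fatigue. If such a shift exists, it adds to the on-minus-off difference in some sessions and subtracts from it in others, according to the order drawn. The design generates the information needed to remove this variation, but the model does not use it.

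The direction of the loss matters. In most analyses, extra noise works against the hoped-for conclusion. Here durability is inferred partly from the absence of a significant interaction, so noise in the interaction tests makes it easier to call the effect durable when it is in fact waning.

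**Working it through.** **1. The plan's own figure.** Section 10.0 states "a sample size of 19 is needed assuming a conservative correlation of 0.3 across evaluation times, for 80% power and 5% significance level", with f = 0.25. For a within-participant effect with m measurements, λ = N·m·f²/(1 − ρ), with m − 1 and (N − 1)(m − 1) degrees of freedom. The plan does not state m. With m = 10 (2 conditions × 5 times), λ = 19 × 10 × 0.0625 / 0.7 = 16.96 on 9 and 162 df, and power is 81.4% (91.2% at N = 24). The figure of 19 reproduces on that reading; m = 5 would give 28. Test order does not enter this calculation, so the point below does not change it.

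**2. One session's difference.** From the documents: 24 participants, 5 evaluation times, 2 conditions. Assumed: one on and one off score per test per session, single-test SD = 1 with independent errors, order drawn at random, and a first-to-second shift L of 0.25 to 1.0 SD. Then on-minus-off = effect ± L + error, the error has variance 1 + 1 = 2, and the total variance is 2 + L².

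| L | Variance | Inflation, (2 + L²)/2 − 1 |
|---|---|---|
| 0 | 2 | 0 |
| 0.25 | 2.0625 | 3.1% |
| 0.5 | 2.25 | 12.5% |
| 0.75 | 2.5625 | 28.1% |
| 1.0 | 3 | 50% |

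**3. Vibration × evaluation time.** Suppose the instant effect wanes linearly, in both conditions, through 0.85, 0.6375, 0.425, 0.2125 and 0 SD. The sum of squared deviations is 0.85² × 0.625 = 0.4516. Averaged over the two conditions, each participant's difference at one time has variance (2 + L²)/2. So λ = 24 × 0.4516 / ((2 + L²)/2) on 4 and 92 df. A participant's stable level of response cancels from this test.

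| L | λ | Power, formula | Power, simulation |
|---|---|---|---|
| 0 | 10.84 | 73% | 72–73% |
| 0.25 | 10.51 | 71.5% | 70% |
| 0.5 | 9.63 | 67% | 68% |
| 0.75 | 8.46 | 61% | 60% |
| 1.0 | 7.2 | 53% | 54% |

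The two columns agree within two points. With a balanced order and position fitted, simulated power is about 73% at every L.

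**4. Vibration × condition.** The same variance applies. Suppose the waning occurs only in the treatment condition, so the mean effects are 0.425 and 0.85 SD and differ by 0.425. With five sessions per condition, the noncentrality is 0.425 / √(2(2 + L²)/(5 × 24)) on 23 df. This is 2.33 at L = 0 (power 61%) and 1.90 at L = 1.0 (power 44%).

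**5. Vibration main effect.** Average all ten sessions, with an effect of 0.5 SD and a participant-by-vibration SD of 0.3 (both assumed). The noncentrality is 0.5 / √((0.09 + (2 + L²)/10)/24). Power is 99.2% at L = 0, 98.7% at L = 0.5 and 96.4% at L = 1.0. A much smaller effect has less headroom. At 0.169 SDs of a single difference (0.169 × √2 = 0.24 single-test SD), with no participant variation, simulated power is 61% with order ignored against 71% with order fitted, when the shift is half the SD of a difference (L = 0.5 × √2 = 0.71).

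**6. Validity and chance imbalance.** Simulated type I error under simple randomisation is 4.8% to 5.3%. Each evaluation time pools 48 pairs. A 2:1 or worse order split at one time has probability 2.9%, and at any of the five 1 − 0.971⁵ ≈ 14%.

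**The case against.** The strongest reply is that randomised, blinded order is already a valid design and what remains is an optional refinement. Much of that stands.

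- **Bias.** A reader might infer that order effects bias the instant effect or create false signs of waning. They do not. Order is randomised, the error rate stays at its nominal level, and chance imbalance is the same quantity as the L² term, not an additional harm.
- **Single-cell figures.** In one visit of one condition (24 sessions), a 16:8 or worse split has probability 15%, and it occurs in at least one of the ten cells with probability 81%. Power for that cell alone falls from about 78% to 61% at L = 1.0. These numbers are correct but describe a test that the plan does not run. The planned tests pool 48 pairs per time, 120 per condition or 240 overall.
- **Fatigue.** The plan does not predict that fatigue will affect scores. It provides breaks, and Section 12.0 calls the risk minor.
- **Silence.** Random order is compatible with a balanced list that is simply not described. Nor do the documents say how many on and off repeats are taken or how they are arranged; repeats or interleaving would change the size of any shift.
- **Size of L.** Nothing in the documents supports a large value, and familiarity over ten visits may shrink practice effects.

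Two things are left. Even a balanced list would not put position into the model. And the interaction tests have little power to spare, in the direction that favours a durability claim.

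**Conclusion.** The point holds as a matter of precision in the secondary aim, not of validity. Order is randomised, balance is not stated, and position is not modelled. Any shift between the two tests therefore inflates the variance of the on-minus-off difference by L²/2 and lowers power for the two interactions.

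The loss is small at L of 0.5 or less (up to about five points of power in the waning example) and material only from about 0.75 upwards. At L = 1.0 the chance of missing the illustrated waning rises from about 27% to about 46%. These figures rest on assumed values of L, the waning pattern, and one on and one off score per session. The main effect has ample power at 0.5 SD or more. The primary aim and the sample sizes of 19 and 24 are untouched.

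The innate-function analysis is affected less. An off score carries extra variance L²/4 on 1, which is 1.6% at L = 0.25 and 6% at L = 0.5.

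**What to change.** **Section 9.0, Durability.** State that on/off order follows a balanced random list: equal numbers on-first and off-first within each visit of each condition, and within each participant across visits as far as possible. Record the order at every session. If such a list already exists, describe it.

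**Section 10.0, durability analysis.** Analyse on/off scores with a linear mixed model that keeps vibration, condition, evaluation time and their interactions, and adds test position (first/second) as a fixed effect. Use the same term when off scores are analysed for innate function. A mixed model is needed because each session fills only two of the four vibration-by-position cells, so position cannot be a crossed factor in the classical ANOVA.

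Both parts are needed. In a single-visit simulation with the shift equal to the SD of one difference, balancing without fitting order gave a type I error of 0.5% and power of 21%, against 53% with order fitted.

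**Cost.** One degree of freedom, if the shift is taken as constant over visits, and a mixed model in place of the classical analysis. There are no extra visits, tests or participants. If there is no shift, essentially nothing is lost. Balance has to be arranged before data collection, and the position term should be specified before unblinding so that it does not look post hoc.
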